7.2 Biological Sample Submissions

All specimens submitted must be entered and tracked via the on-line ECOG-ACRIN Sample Tracking System (STS)

	Pre-Treatment 1	Day 28 to 35 (Remission)	Submit To:
MANDATORY: Bone Marrow Aspirate (Heparin, First Pull) ^{2,3}	X	X	LTRL
MANDATORY (Only if Bone Marrow Aspirate not submitted): Peripheral Blood (heparin, green or purple [EDTA] top tubes, 30-40mL) ³	X ⁴		LTRL
From patients who answer "Yes" to "I agree to provide additional samples for research."			
Bone Marrow Smears (Wright-Giesma Stained)	X	X	LTRL

1. Signed EAI141 patient consents and HIPAA authorizations must be submitted to the ECOG-ACRIN Leukemia Translational Research Laboratory (LTRL) prior to or at the time of submission of the bone marrow to the LTRL.
2. The laboratory will accept any amount of bone marrow as long as it represents a first pull. Ideally, 2-3mL of aspirate from a separate aspiration site should be submitted. For the MRD assessments, aspirate from a separate bone marrow aspiration site must be submitted. ONLY SUBMIT ASPIRATES FROM THE FIRST PULL OF AN ASPIRATION SITE FOR MRD TESTING. DO NOT SUBMIT ASPIRATES FROM THE SECOND OR THIRD PULL OF THE SAME ASPIRATION SITE. For patients with an insapirable bone marrow ("dry tap"), or if a bone marrow has been done previously and that patients refuses another aspiration done, call [name] laboratory at [contact] to discuss the case and the possibility for submitting peripheral blood only. Be prepared to report the WBC count and the blast count in the peripheral blood at the time of the call.
3. Leftover samples will be stored for future undefined research studies from patients who answer "YES" to "My samples and related information may be kept in a Biobank for use in future health research."
4. Peripheral blood can be submitted after registration to Step 1 to coincide with clinical assessments performed prior to protocol specified imaging. Peripheral blood must be submitted only if bone marrow aspirate will not be submitted at preregistration.

8. Agent Formulation and Procurement

NCI Supplied Agent(s) – General Information

8.1 Supplier of the FLT Agent

8.1.1 Drug Ordering

FLT will be supplied by a commercial vendor of radioisotopes in most cases. The vendor must be authorized within the NCI IND, and the site had been qualified for production by NCI and ECOG-ACRIN. FLT can only be synthesized on site if the chemistry manufacturing and control procedures are filed within the NCI IND and the site has been approved for FLT production under the NCI IND and notified of approval by the NCI Cancer Imaging Program. All other sites will be required to use an approved commercial supplier.

The investigational pharmacist or qualified nuclear medicine technologist at the participating institution will be the responsible party for receiving the FLT, as designated by the site principle investigator.

8.1.2 Drug Returns

If for any reason the study imaging is unable to be completed, sites will allow the radioactivity of the FLT solution to decay and then discard it appropriately per site's policies and procedures. A copy of the policy should be available upon request.

8.1.3 Drug Accountability

The investigator or the investigator-designee must maintain a detailed record of receipt, disposition, and destruction dates of FLT solution, using the Drug Accountability Record form available through CTSU.

In accordance with regulations, the radioisotope vendor conducts several quality control tests on the FLT product prior to release for human administration. Once delivered to the participating institution, doses will be stored in the appropriate storage area in the nuclear medicine facility until they are administered to the patient.

8.2 ¹⁸F-FLT

For complete information, please refer to the Investigator's Brochure:

"3'-deoxy-3'-[F-18] fluorothymidine: [F-18]FLT, An Investigational Positron Emission Tomography (PET) Radiopharmaceutical for Injection and intended for use as an *in vivo* diagnostic for imaging active cellular proliferation of malignant tumors", Edition Number 7, Edition date 2009.

8.2.1 Other Names

3'-deoxy-3'-[F-18] fluorothymidine, [F-18]FLT, FLT

8.2.2 Classification

Investigational new drug: Radiopharmaceutical/radiotracer

8.2.3 Mode of Action
The pharmacology of FLT as a therapeutic agent is based on its action as an inhibitor of DNA synthesis. As a diagnostic imaging agent, phosphorylation by thymidine kinase leads to tracer retention in proliferating tissue.

8.2.4 Storage and Stability
In accordance with regulations, the radioisotope vendor conducts several quality control tests on the FLT product prior to release for human administration. Once delivered to the participating institution, doses will be stored in the appropriate storage area in the nuclear medicine facility until they are administered to the patient.
The drug solution is stored at room temperature in a gray butyl septum sealed, sterile, pyrogen-free glass vial and has an expiration time of 8 hours.

8.2.5 Dose Specifics
The administered activity will be 0.07 mCi/kg with a maximum of 5 mCi. The amount of injected drug is \leq 6.1 μ g (\leq 25 nmol per dose) of FLT.

8.2.6 Preparation
The injectable activity of FLT for most studies will be \leq 0.07 mCi/kg of fluorine-18, not to exceed 5 mCi with a specific activity greater than 200 Ci/mmol at the time of injection. In the dose of FLT, only a small fraction of the FLT molecules are radioactive.

Rev. Add3 8.2.7 Route of Administration
FLT is administered to subjects by intravenous injection. There is no evidence that nonradioactive and radioactive FLT molecules display different biochemical behavior.

8.2.8 Incompatibilities
N/A

8.2.9 Availability
8.2.9.1 Drug Ordering
There are two ways to obtain the FLT agent for this study:
1) Commercial vendor supply
2) On-site manufacturing
1) Commercial Vendor Supply. FLT may be supplied by a commercial vendor of radioisotopes if authorized and approved by the NCI CIP. Please see informational document posted on the CTSU regarding FLT dose supply for a listing of the approved commercial vendors and process for set up. The investigator or the investigator-designee will order patient doses of FLT. The investigative

radiopharmaceutical FLT solution will be shipped to the site the same day the participant is to be injected.

2) On-Site Manufacturing. FLT can be manufactured on-site *only* after the site had been qualified and approved for production by NCI Cancer Imaging Program (CIP) and ECOG-ACRIN. For additional information about on-site manufacturing, see "*Regulatory approach to approve manufacturing sites to make IND PET agenda to be used under a Cancer Imaging Program (CIP IND for a specified trial)*".

The investigational pharmacist or qualified nuclear medicine technologist at the participating institution will be the responsible party designated by the investigator.

8.2.9.2 Drug Returns

If for any reason the study imaging is unable to be completed, sites will allow the radioactivity of the FLT solution to decay and then discard it appropriately per site's policies and procedures. A copy of the policy should be available upon request.

8.2.9.3 Drug Accountability

The investigator or the investigator-designee must maintain a detailed record of receipt, disposition, and destruction dates of FLT solution, using the Drug Accountability Record form.

https://ctep.cancer.gov/forms/docs/agent_accountability.pdf

Rev. Add3

8.2.10 Side Effects

See Section [5.5](#) for side effects.

8.2.11 Nursing/Patient Implications

Standard safety precautions required when handling radioactive materials, predominantly during the injection and uptake period should be followed. FLT requirements are similar to those used for other PET tracers, such as FDG.

9. Imaging Protocol

9.1 FLT PET Imaging Studies

Specific image acquisition and reconstruction protocols will be made available through the CTSU. Instructions for images submission is provided in Section [4.10](#).

9.2 FLT Administration

FLT will be synthesized according to the standard operating procedures provided by the NCI. A summary of the synthesis procedure and associated quality control can be found in the investigator's brochure.

FLT will be administered in the PET imaging suite under physician supervision. The imaging technologist or nurse will administer the FLT by intravenous infusion over one minute, followed by a saline flush. A fully equipped emergency cart and ACLS certified personnel will be available. Reported adverse events and potential risks are described in Section [5.5](#). The infusion and imaging procedure will be terminated in any patient who exhibits anaphylaxis, chest pain, dyspnea, or grand mal seizure.

9.3 Timing of FLT PET Studies

Two imaging sessions, an *optional* baseline and *mandatory* post-treatment will be performed (see Study Procedures Table).

Optional Baseline: The optional baseline FLT PET/CT imaging must be completed within one week prior to beginning of induction chemotherapy.

Mandatory Post-Treatment: Post-treatment FLT PET/CT must be done after the completion of the induction chemotherapy and **within 3 days before or after nadir bone marrow** (approximately Days 10-17 after the initiation of the first cycle of the chemotherapy and prior to re-induction if required).

9.4 Imaging Quality Assurance (QA)/Quality Control (QC) Procedure

Participant must be scanned on PET/CT scanners that have been qualified by the ACR Imaging Core Laboratory per the protocol-specific instructions made available to participating sites.

Qualification Utility for the Imaging Core Laboratory (QUIC) is the web-based tool for managing the qualification process and communicating with the core lab staff. The QUIC User Guide will be made available to participating sites.

Refer to the instructions about uploading images and completing the required application forms.

A hybrid PET/CT scanner is mandatory. The ability to calculate standardized uptake values (SUVs) is also mandatory. All sequential imaging sessions should be performed on the same PET/CT scanner, whenever possible. Any deviations should be reported to ECOG-ACRIN. QA/QC procedures will include review of DICOM files against study protocols. The PET/CT scanner must be kept calibrated in accordance with the manufacturer's recommendations. The scanner should routinely be assessed for quantitative integrity and stability by being tested using various imaging protocols on a standard phantom. For SUV

measurements, this assessment should include a comparison against a dose calibrator to ensure accuracy; that is, a comparison of the absolute activity measured versus the measured activity injected, should be performed.

A daily QC check must be performed at the beginning of the day, including PET/CT scanner and dose calibrator, in accordance with the manufacturer recommendations. If any of the QC results are outside of the manufacturer's guidelines, the study must be rescheduled and the problem rectified before scanning any patients.

Rev. 7/17

9.5 Imaging Sessions

The participant will report to the PET suite and undergo FLT injection. Approximately 60 minutes (\pm 10 min) after injection, a static whole body image will be acquired. If both optional baseline and mandatory post-treatment FLT PET/CT scans are completed, the participant should be scanned on the same scanner for each session. The whole body scan (top of the head [vertex] to below the knees) will be obtained. Details of the imaging procedure are specified in the Site Imaging Manual.

9.6 Supportive Care Guidelines

Any adverse effects, related or non-related to the injection of FLT, will be treated as clinically indicated with no study-related restrictions.

9.7 Dosing Delays/Dose Modifications

9.7.1 FLT Dose

The dose of FLT is based on the radiation dosimetry estimates. Due to the potential of a poor radiosynthetic yield or unavoidable time delays, a lesser amount of radioactivity may be administered at the discretion of the site PI, based on whether clinically acceptable images can be acquired with the dose administered. Any such modifications of the agent infusion will be recorded.

9.8 FLT PET/CT Image Analysis: Central Read

Quantitative Total Marrow Imaging (QTMI) image analysis will be performed at a central analysis laboratory and will include extraction of the whole bone marrow proliferative activity as assessed by analysis of the full FLT PET/CT images as follows [5]:

- The CT images are thresholded to extract the bone;
- These CT bone volumes are expanded to include the marrow resulting in bone + marrow CT masks;
- The masks are applied to the PET images to isolate the PET voxels representing the bone and marrow;
- An SUV threshold of 0.5 is applied to the masked PET images to extract the marrow PET voxels, yielding PET images of the bone marrow.

After the extraction of the spatial bone marrow compartment from the FLT PET/CT imaging, the FLT uptake reflecting the rate of bone marrow proliferation across the bone marrow is analyzed. Preliminary data suggests that image analysis should ideally include analysis of the whole bone marrow to determine a

number of bone marrow proliferation parameters, such as the mean proliferation, maximum proliferation, as well as heterogeneity of proliferation. While each of the proliferation parameters appears predictive of the clinical outcome, each of these parameters likely has different performance characteristics, making them more or less suitable for clinical use.

The extraction analysis will include three imaging parameters (SUV_{mean} , SUV_{max} , SUV_{hetero}).

- Maximum FLT uptake (SUV_{max}), defined as the maximum FLT uptake across the total bone marrow compartment
- Mean FLT uptake (SUV_{mean}), defined as the mean FLT uptake across the total bone marrow compartment
- Heterogeneity of FLT uptake (SUV_{hetero}), defined as the coefficient of variation of FLT uptake across the total bone marrow compartment

While all of these parameters will be extracted and analyzed for each patient, only SUV_{max} will be used as the primary endpoint in the statistical analysis. All other parameters will be used and reported in descriptive manner (see **Statistical Considerations**).

Rev. 10/16

9.9 Other Comparators

9.9.1 Pathologic Response

This nadir or “day 14 bone marrow” is recommended in the 2012 National Comprehensive Cancer Network (NCCN) Guidelines for the treatment of AML. The ideal response by the NCCN is defined as a hypoplastic marrow with < 10-20% cellularity and < 5-10% residual blasts. This biopsy is a standard measure of induction chemotherapy effectiveness. The results of this analysis will be reported.

9.9.2 Clinical Response

Clinical response will be assessed as below. Criteria are based upon the standard AML response criteria as published by Cheson et al [4]. Remission bone marrow will be performed per standard clinical practice, typically at Day 28-35 after treatment began and upon count recovery. The results of this analysis will be reported.

Table 1. Clinical Response Criteria

Response	ANC (cells/uL)	Platelet Count (cells/uL)	Bone Marrow Blasts (%)
CR	> 1000	> 100,000	< 5%
CRI	> 1000	> 50,000	< 5%
PR	> 1000	> 100,000	> 5% and < 25% and 50% less than pre-therapy
LFS	Any	Any	< 5%
RD			> 5%, not attributable to marrow regeneration

Abbreviations: CR (complete remission), CRI (complete remission with incomplete platelet recovery), PR (partial remission), LFS (leukemia-free state), RD (resistant disease)

Rev. 10/16

9.10 Data Analysis

The primary goal of our endpoints will be to evaluate the negative predictive value (NPV) of post-treatment FLT PET/CT imaging for complete remission in patients receiving induction chemotherapy for AML. Additional comparisons with imaging, pathologic, clinical and outcome data will also be performed. These comparisons are summarized in Table 2.

Table 2. Planned Comparisons with FLT Parameters

FLT Parameters	Compared To
OPTIONAL Baseline FLT uptake parameters (FLT-base)	CR, RD Nadir bone marrow, relapse-free and overall survival
Post-treatment FLT uptake parameters (FLT-post)	CR, RD Nadir bone marrow, relapse-free and overall survival
Change in FLT uptake parameters (FLT-post vs FLT-base)	CR, RD Nadir bone marrow, relapse-free and overall survival

9.11 Image Analysis

A central review and analysis of all FLT PET/CT imaging will be performed at the ACR Imaging Core Laboratory in coordination with the University of Wisconsin Image Analysis Core (IMAC). The centralized imaging analysis will be used for endpoint calculations. Radiologists will perform local reads of the images to help guide central review. Central review will subsequently be completed; data will be shared at the culmination of the study.

10. Statistical Considerations

The overall objective of this trial is to evaluate the negative predictive value of post-treatment FLT PET/CT imaging for complete remission (CR) in comparison with blast counts from bone marrow biopsy (BMBX) at Day 14.

Definition of complete remission (CR): The CR designation requires that the patient achieve the morphologic leukemia-free state and have an absolute neutrophil count of more than 1,000/uL and platelets of greater than 100,000/uL. Hemoglobin concentration or hematocrit has no bearing on remission status, although the patient must be independent of transfusions. Occasionally, a rare peripheral blood blast may be identified during regeneration; however, if the patient is in CR, the bone marrow would have less than 5% blasts and no Auer rods [4].

Definitions of FLT Positivity and Negativity for CR:

- FLT PET “positive” $\rightarrow \text{SUV}_{\max} \leq 7$
- FLT PET “negative” $\rightarrow \text{SUV}_{\max} > 7$

The post-treatment FLT PET/CT needs to be conducted **within three days** before or after the nadir bone marrow biopsy (between Days 10-17 after initiation of first induction cycle and prior to reinduction). After the imaging analysis to collect SUV_{\max} , we define a positive testing result as a low uptake value, which corresponds to the lower blast count in the BMBX.

Our primary aim is to evaluate the negative predictive value (NPV) of post-treatment FLT PET/CT imaging for achieving CR in patients receiving induction chemotherapy for AML. The results of the pilot study [5] show that there was a clear separation between responders and non-responders in terms of SUV measurements from FLT PET/CT imaging. For example, the means (standard deviation [SD]) of SUV_{\max} for responders and non-responders are 3.6 (0.2) and 11.4 (0.8), respectively. Using the Newton-type algorithm, we found the best cutting point is around $\text{SUV}_{\max} = 7$. This optimization was done using the *nlm* function in R package *stats*. Thus, our FLT PET data will be dichotomized at $\text{SUV}_{\max} = 7$ whereas positive FLT PET testing results will be the ones with $\text{SUV}_{\max} \leq 7$ and the negative FLT PET testing results will be the ones with $\text{SUV}_{\max} > 7$.

Our sample size calculation is based on hypothesis testing to see if the NPV of post-treatment FLT PET/CT is significantly better than that of the Day 14 bone marrow biopsy. The CR rate is assumed to be around 50% in the study population. In addition, we assume that the FLT PET-positivity rate in the study population is around 50% as well. Under these assumptions, we will need 21 FLT-negative patients to have the power of 80% to test if the NPV of FLT is higher than 0.64 (null hypothesis) given that the true NPV of FLT is 85% or above (alternative hypothesis). The test is one-sided with the target 0.10 significance level. The Exact Binomial test in PASS 2012 was used for the calculations [6]. Since the positivity rate is assumed to be around 50% in the study population, we need to enroll 42 patients. Due to the random nature of the observed numbers of patients meeting the clinical criteria in a prospective study, a sample size correction technique attributed to Pepe (2003) was applied. Our calculation shows that after adding 9 extra patients, we can be 90% sure to yield the required numbers of patients meeting the clinical criteria, which brings the sample size to 51. After an additional 10% inflation to account for potentially incomplete data, we arrive at an overall

sample size of 57 participants. The sample size is 86 evaluable if the true NPV of FLT PET/CT is 80% or above. The sample size is 38 if the true NPV is 90% or above.

Rev. Add3

According to our interim monitoring of the early enrollment, the attrition rate is around 38%. The main reason was attributed to the failed remission bone marrow biopsy due to poor health or death. This accounted for ~1/2 of attrition. In addition, there were ~1/3 of attrition due to the failure of completing the post-treatment FLT PET/CT scans (e.g., equipment failure, patients withdrew). We will closely monitor these issues and the enrollment may stop early if we observe a lower attrition rate. Thus, **the overall sample size is up to 83 participants.** The below table shows the required number of participants at various attrition rates.

Attrition rate	Sample size
10%	57
25%	68
38%	83

Futility Analysis

A futility analysis will be performed when half of the analyzable participants have completed the trial. The method of conditional power [7] will be used for the futility analysis, which will estimate the probability that NPV with all subjects would be greater than 0.64, conditional on the results accumulated at the time of the futility analysis. If this probability is too small (i.e., < 0.20), implying that it is unlikely that the FLT PET/CT is useful, then a decision may be made to terminate the study early.

Objectives

Rev. 10/16

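### The 80% power claimed at 83 participants holds only if attrition is unrelated to remission, although about half of that attrition is death or poor health

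*Combined protocol and SAP*

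**What the plan says.** Section 10 (Statistical Considerations) sizes the primary test on the FLT-negative patients: "we will need 21 FLT-negative patients to have the power of 80% to test if the NPV of FLT is higher than 0.64". The alternative is "given that the true NPV of FLT is 85% or above (alternative hypothesis". On the test itself: "The test is one-sided with the target 0.10 significance level" and "The Exact Binomial test in PASS 2012 was used for the calculations".

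Two inputs turn 21 FLT-negatives into a total: "The CR rate is assumed to be around 50% in the study population", and "we assume that the FLT PET-positivity rate in the study population is around 50% as well". That gives 42 to enrol. Nine more patients, added for 90% assurance of reaching the required number, make 51, and a 10% allowance for incomplete data makes 57.

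The Addendum 3 paragraph replaces the 10% by an observed attrition of about 38% and sets the total at up to 83. On the cause it says: "The main reason was attributed to the failed remission bone marrow biopsy due to poor health or death". It gives this as about half of the attrition, and failure to complete the post-treatment scan as about a third. The attrition table lists 57, 68 and 83 participants at 10%, 25% and 38%.

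Section 10 has no rule for classifying a scanned patient who dies, or is too ill, before the remission marrow. Section 4.11 covers only patients who complete neither scan.

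**The concern.** Dividing by one minus the attrition rate restores the number of evaluable patients. It restores their composition only if those lost resemble those kept. A patient who dies before the remission marrow cannot be documented in CR, and a patient too ill for it is plausibly less likely to be. Counting these patients as attrition to be replaced implies that they are left out of the NPV.

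In this trial a correct FLT-negative result is one in a patient who does not reach CR. Losing non-CR patients therefore does two things: it leaves fewer FLT-negatives, and it lowers the share of FLT-negatives that are correct. The second effect moves the true NPV of the analysed set towards the null of 0.64. A non-significant primary result could then be read as FLT failing an 80%-powered test when the power was lower.

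**Working it through.** **Inputs from Section 10.** Null NPV 0.64; alternative 0.85; one-sided 0.10, exact binomial; 50% CR; 50% FLT-positive; 51 evaluable; 38% attrition, about half of it death or poor health (0.38/2 = 0.19 of enrolled).

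**Step 1: the plan's figures reproduce.** With 21 FLT-negatives the test rejects at 17 or more correct: size 0.078, power 0.803. P(at least 21 of 51 at 50%) = 0.92. Inflation: 51/0.90 = 56.7, giving 57; 51/0.75 = 68; 51/0.62 = 82.3, giving 83.

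**Step 2: accuracy implied by the inputs.** With half FLT-negative and NPV 0.85, 0.5 × 0.85 = 0.425 of patients are FLT-negative and non-CR. Since 0.50 are non-CR, specificity for CR is 0.425/0.50 = 0.85. Sensitivity is 0.85 by the same arithmetic.

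**Step 3: split the loss at 83 enrolled.** Assume 50% CR among enrolled and that the other 19% is lost at random. Then 83 × 0.81 = 67.2 remain before the death or poor-health loss: 33.6 CR and 33.6 non-CR. That loss is 83 × 0.19 = 15.8 patients. Let *s* be the share of them who are non-CR:

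- analysed CR = 33.6 − 15.8(1 − *s*)
- analysed non-CR = 33.6 − 15.8*s*

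**Step 4: scenario A, FLT accuracy kept and NPV allowed to change.** Two FLT mixes among the lost are shown.

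- *Proportional*: FLT-negatives = 0.15 × CR + 0.85 × non-CR, and NPV = 0.85 × non-CR / FLT-negatives.
- *Favourable*: all 0.15 × 33.6 = 5.0 FLT-positive non-CR patients are among the lost, so every remaining non-CR patient is FLT-negative. Any lost CR patients keep the proportional mix.

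Average power is the exact power averaged over an FLT-negative count distributed Binomial(83, expected count/83).

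| *s* | FLT mix of lost | CR / non-CR analysed | Expected FLT-negatives | NPV | P(at least 21) | Average power |
|---|---|---|---|---|---|---|
| 50% | proportional | 25.7 / 25.7 | 25.7 | 0.85 | 0.89 | 0.83 |
| 80% | proportional | 30.5 / 21.0 | 4.6 + 17.8 = 22.4 | 0.80 | 0.68 | 0.535 |
| 80% | favourable | 30.5 / 21.0 | 4.6 + 21.0 = 25.6 | 0.82 | 0.89 | 0.71 |
| 100% | proportional | 33.6 / 17.8 | 5.0 + 15.2 = 20.2 | 0.75 | 0.46 | 0.31 |
| 100% | favourable | 33.6 / 17.8 | 5.0 + 17.8 = 22.9 | 0.78 | 0.72 | 0.47 |

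**Step 5: which effect costs the power (*s* = 100%).** With the reduced counts (20.2 and 22.9) but NPV 0.85, average power is 73% and 78%. With the planned count (25.7) but the reduced NPVs (0.75 and 0.78), it is 38% and 51%. Most of the loss comes from the lower NPV.

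**Step 6: scenario B, NPV fixed at 0.85 in the analysed set, *s* = 100%.** With perfect PPV, the 17.8 non-CR patients allow 17.8/0.85 = 21.0 expected FLT-negatives: P(at least 21) = 0.54, power 75%. With PPV 0.85 and 51.5 analysed, solving 0.85*x* + 0.15(51.5 − *x*) = 17.8 gives *x* = 14.5: P(at least 21) = 0.05, power 60%. At *s* = 80% the power is 71-81%.

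**The case against.** **The shift is assumed, not observed.** This stands. A reader might infer that 83 enrolled fails to deliver the 50% FLT-negative mix, or that the trial has 31% power. The documents support neither, because they give no CR or FLT status for the patients lost. If half of the lost are non-CR and their FLT mix is like that of the rest, nothing is lost.

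**The FLT-negative share could even rise.** Holding NPV at 0.85 and letting the FLT-negative share of the lost vary from none to all, average power runs from 91% to 68%. The upper end cannot be reached if the lost are non-CR. Under the plan's inputs only 5.0 FLT-positive non-CR patients are available to lose, so at least 15.8 − 5.0, about 10.7 before rounding (68% of the 15.8), must be FLT-negative. It remains possible if many of the lost were on course for CR.

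**The 50% inputs may already describe evaluable patients.** They are used to reach 51 before any allowance for incomplete data, and the population they refer to is not defined. On that reading 51 evaluable patients keep the planned mix and the power stands. Against it, the plan uses the positivity rate to set the number to enrol. The text does not settle this.

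**The attrition is disclosed and will be monitored.** True, and every stated figure reproduces, so this is not an arithmetic error. But monitoring the attrition rate does not deal with who is lost.

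**Conclusion.** The concern holds as a point about what the power statement depends on. The 80% power and the 90% assurance of 21 FLT-negatives are valid at 83 if loss is unrelated to CR and FLT result. The plan does not state that condition, and its own account of the attrition makes it doubtful.

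The size depends on *s*, which the documents do not give. Against a baseline average of about 83%, scenario A gives 54-71% if 80% of those lost to death or poor health are non-CR and 31-47% if all are. Scenario B gives about 60-75% if all are. The two scenarios assume different true NPVs in the analysed set and should not be merged into one range. All these figures assume 50% CR among enrolled and that the other half of the attrition is random; scenario A also uses sensitivity and specificity of 0.85. The main mechanism is a lower complete-case NPV, with fewer FLT-negatives second.

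**What to change.** In the Addendum 3 paragraph and attrition table of Section 10:

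1. Show death or poor-health loss separately from scan failure and other loss.
2. State whether the 50% CR and 50% FLT-positivity refer to enrolled or evaluable patients.
3. State that the 80% power is conditional on loss unrelated to outcome.
4. Give power and the probability of at least 21 FLT-negatives at 83 under two labelled scenarios (NPV changed; NPV fixed at 0.85), narrowed with the interim attrition data already held.

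In Section 10.1, add a sensitivity analysis of the primary NPV that counts scanned patients without a remission marrow because of death or poor health as not in CR. Every FLT-negative patient it adds counts as correct, so it can only raise the estimate or leave it unchanged. It should be reported beside the complete-case result and not replace it.

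The cost is one rewritten paragraph, one table, one extra analysis and a less favourable power statement. No patients or procedures are added.
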